This project will fill several knowledge gaps by characterizing the underlying mechanisms and metabolic signatures of stress hyperglycemia with the use of comprehensive metabolic profiling methods and provide proof-of principle with the use of novel therapies for the prevention and management of stress-hyperglycemia.

Aim 1. To examine baseline and postoperative metabolic profiles of non-diabetic CABG patients with stress hyperglycemia. With a case-control design we will conduct the following analyses:

1.1 Targeted Approach: To determine cross-sectional and longitudinal changes of BCAA, ceramides, acylcarnitines, inflammatory markers, and a biomarker panel for CV risk [CRP + FDP + HSP-70, SuPAR] and their relationship with stress hyperglycemia (BG >140mg/dl) and insulin resistance estimates. *We hypothesize that elevated ceramides, acylcarnitines, branched-chain amino acids (BCAAs) are associated with incident stress hyperglycemia, and that hyperglycemia leads to changes in path-specific biomarkers related to CV risk.*

1.2 Untargeted Analysis: Utilizing untargeted HRM analyses, we aim to identify additional candidate metabolites and metabolic pathways associated with incident stress hyperglycemia during cardiac surgery. *We hypothesize that known (candidate metabolites) and previously unrecognized metabolites and pathways are associated with hyperglycemia during surgical stress.*

1.3 Integrative analysis: Metabolome-wide association studies (xMWAS) and integrative network analyses will be conducted to find multilevel associations between metabolites, biomarkers, and stress-hyperglycemia. *We hypothesize that multiple factors associated with diabetes and cardiovascular disease are interrelated and predict hyperglycemia during stress conditions.*

Aim 2. To obtain preliminary estimates of the effect of a long-acting GLP-1 RA on the prevention of stress-hyperglycemia and modulation of metabolic stress during cardiac surgery. We propose a randomized study with assignment to dulaglutide or placebo three days prior to surgery in non-DM obese patients (BG<126 mg/dL, HbA1c <6.5%, BMI \geq 25, age \geq 40 years) undergoing CABG surgery.

2.1 Primary endpoint: to determine if dulaglutide can prevent stress-hyperglycemia.

2.2 Secondary endpoints: to determine if dulaglutide can result in a lower mean BG during ICU and hospital stay. We will also explore the need of rescue therapy with insulin and differences in clinical outcomes.

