With advanced data extraction provided by xMSanalyzer and apLCMS, I will be able to also measure a spectrum of high and low abundance metabolites. We will utilize a well-established computational metabolomics workflow with rigorous standard operating procedures outlined in Fig. 7.¹²⁴ Data Selection and Annotation (Biostatistics and Bioinformatics Tools): HRM data will be processed using apLCMS with xMSanalyzer^{125,126}. Feature annotation will be performed using xMSannotator.¹²⁷ xMSannotator provides confidence scores for more than 2,000 metabolites, with more than 300 metabolites having confirmed identities and including most major pathways. The quality of data will be judged based on established rigorous criteria (e.g. coefficient of variation within replicates and QC samples, the percentage of missing values, the percentage of data exceeding detection limits of the machinery, batch-effects, and the percentage of outliers, etc.). Principal Component Analysis (PCA) will be used for batch-effect evaluation and ComBat¹²² will be used for batch- effect correction if necessary. Identifying expressed metabolites across different time points: we will use univariate and multivariate statistical methods, such as linear mixed effects models with post-hoc Tukey tests, LIMMA, and multilevel sparse Partial Least Squares Discriminant Analysis (msPLSDA).^{128,129} Multiple hypotheses testing correction will be performed using the Benjamini-Hochberg method.¹³⁰ Identifying putative biomarkers: we will use a consensus feature selection approach such that metabolic signatures identified by both univariate and multivariate approaches will be used for downstream analyses. K-fold and leave-one-out cross-validation using Support Vector Machine (SVM) will be performed to evaluate predictive accuracy of putative biomarkers. Two-way hierarchical clustering analysis will be performed to identify clusters of correlated metabolic features and to evaluate the ability of the discriminatory features to separate samples based on stress-hyperglycemia. Pathway enrichment analysis: Pathway analysis will be performed with pathway enrichment software for untargeted metabolomics data (Mummichog and MetabNet)^{131,132}. Where appropriate, additional chemical verification will be performed for significant metabolites of interest according to retention time and characteristic ion dissociation (MS/MS) patterns relative to authentic standards. Metabolome-wide association study (MWAS) of specific metabolites will be conducted (MetabNet) to facilitate detection of their related metabolic pathways and network structures in association with glucose levels (continuous) and stress-hyperglycemia as a discrete dichotomous variable.

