
Expected outcomes of Aim 1: During our analysis of candidate metabolites and discovery phase in Aim 1 we expect to find an association between candidate metabolites (i.e. BCAA, ceramides, acylcarnitines) and pathways associated with stress-hyperglycemia. We also expect to find an association between pathway-

specific biomarkers and stress-hyperglycemia with a higher degree of association according to the number of biomarkers based on pre-specified cut points (biomarker risk score).⁶⁶ We expect to find multilevel associations between glucose, biomarkers and candidate metabolites. Serial measurements including measurements before the acute stress episode will facilitate causal interpretations.

Potential Pitfalls, and Alternative Considerations: It is possible that some comparisons do not yield false discovery rate (FDR)-significant metabolites. In this scenario, and to provide a balance between type I and type II statistical error, metabolites with raw $p < 0.05$ will be used for subsequent analyses, with statistical tests for pathway enrichment. Pathway enrichment analysis is less susceptible to type II error.¹³⁴ We hypothesize that stress-hyperglycemia leads to elevation of path-specific biomarkers, however it is possible that pre-surgical elevation of biomarkers predicts the development of stress-hyperglycemia. Elucidating this scenario is important as identifying susceptible subjects before surgery (baseline elevation of biomarkers) will facilitate the design of cohort studies as well as recruitment of at-risk patients in future trials.

D2. Randomized Clinical Trial

Aim 2. To obtain preliminary estimates of the effect of a long-acting GLP-1 RA on the prevention of stress-hyperglycemia and modulation of metabolic stress during cardiac surgery.

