Analytic Techniques: Glucose levels will be analyzed by the hexokinase method (Beckman-Coulter, Los Angeles, CA). Insulin and C-peptide levels will be measured by two-site sequential chemiluminescent immuno-metric assays as previously described. Surrogates of beta cell function (HOMA-B) and insulin resistance (HOMA-IR) will be derived from fasting glucose, c-peptide and insulin. Only glucose and c-peptide will be measured serially after surgery (given high likelihood of exposure to exogenous insulin).

Analysis: We will integrate analyses from Aims 1 and Aims 2 to evaluate the role of dulaglutide on metabolites, metabolic pathways and biomarkers. We will use univariate and multivariate statistical methods, such as linear mixed effects models with post-hoc Tukey tests, LIMMA, and multilevel sparse Partial Least Squares Discriminant Analysis (msPLSDA), as described in Aim 1.

Expected outcomes in Aim 2: In Aim 2.1 we expect to observe a decrease in the number of patients with stress-hyperglycemia with low risk of hypoglycemia with dulaglutide therapy. We expect to find a least an 18 mg/dl (1 mmol/l) mean difference in BG between groups during ICU stay. In Aim 2.2 we don't expect to find differences in hospital outcomes. In Aim 2.3 We expect to observe differential changes in up or down regulation of metabolic pathways in response to dulaglutide compared to placebo.

Potential Pitfalls, and Possible Solutions, Alternative Consideration: Recruitment and retention of patients are important challenges in RCTs; however, Emory University and affiliated hospitals serve as cardiovascular referral center to a large population in the city of Atlanta, with over 1,000 major cardiac surgeries performed yearly. In our previous trial we recruited 340 patients over 3 years, therefore we expect to have enough time during the award period to complete enrollment (please see research timeline). It is possible that dulaglutide does not have an effect on the prevention of hyperglycemia. This information will help us understand the contribution of the incretin pathway to glucose metabolism during surgical stress.

E. Risks to Human Subjects

E.1.1 Human Subjects Involvement, Characteristics, and Design

- Description and justification for proposed involvement of human subjects:**

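### Aim 1.2: the only multivariate selector named removes each patient's mean, so the both-methods rule would drop case/control differences that are constant over time

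*Combined protocol and SAP*

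**What the plan says.** Aim 1 is stated as "To examine baseline and postoperative metabolic profiles of non-diabetic CABG patients with stress hyperglycemia", and Aim 1.2 looks for metabolites and pathways linked to incident stress hyperglycemia. Cases are defined by the glucose value on arrival in the ICU (section D1, Study design; section E.1.1, Group Assignment / Case Definition). Case status is therefore fixed within a patient. Samples are taken at five times: baseline, intraoperative, 24 hours, 72 to 96 hours and 30 days. The first two precede the classification.

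For feature selection, Aim 1.2 writes "Identifying expressed metabolites across different time points: we will use univariate and multivariate statistical methods, such as" and then lists "linear mixed effects models with post-hoc Tukey tests, LIMMA, and multilevel sparse Partial Least Squares Discriminant Analysis (msPLSDA". The next step is a "consensus feature selection approach such that metabolic signatures identified by both univariate and multivariate approaches will be used for downstream analyses". Those later steps include cross-validated support vector machines and a clustering meant to "evaluate the ability of the discriminatory features to separate samples based on stress-hyperglycemia". The same text appears a second time in section D1. The class label for the multilevel method (case/control, time, or their combination) is not given.

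The Aim 2.3 analysis (section D2) reuses the list: "LIMMA, and multilevel sparse Partial Least Squares Discriminant Analysis (msPLSDA), as described in Aim 1". It does not restate the consensus rule.

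**The concern.** Mixed models and LIMMA are fitted one feature at a time, so they are the univariate side of the consensus rule. Principal components, support vector machines and clustering are named for batch checks, predictive accuracy and grouping, not for selection. That leaves multilevel sPLS-DA as the only multivariate selector in the text. It works on within-patient variation, while part of the Aim 1.2 question lies between patients: which metabolites differ between future cases and controls, including before surgery.

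Because the rule is an intersection, a feature that one side cannot see is lost however clearly the other side sees it. A metabolite that is higher in cases before surgery and stays higher would be missing from the untargeted signature. The accuracy and clustering results would then describe a feature set from which that kind of signal had been removed by construction.

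**Working it through.** **Context from the plan.** The plan gives no figure for the selection step. Section E.1.9 sizes Aim 1 at N=50 for a Wilcoxon test, effect size above 1, alpha 0.05 and power 0.80. Taking the test as two-sided with 25 per group, the number needed per group at an effect of 1 is:
- normal approximation: 2 × (1.960 + 0.842)² / 1² = 15.7, so 16;
- t-test: 16.7, so 17;
- Wilcoxon: 16.7 / (3/π) = 17.5, so 18.

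With 25 per group, power is 93% (t-test) or 92% (simulated Mann-Whitney). For one uncorrected test, a 1 SD difference is within reach. The question is whether the pipeline keeps it.

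**Algebra.** Let x_ij be a feature in patient i at time j, and g_i the case label. The multilevel step replaces x_ij by w_ij = x_ij − x̄_i.
- A shift δ·g_i that is equal at all times adds δ·g_i to both x_ij and x̄_i, so it cancels in w_ij whatever label is used afterwards.
- With label g_i, the cross-product is Σ_i g_i Σ_j w_ij = Σ_i g_i × 0 = 0 for every feature. A missing sample does not change this, because each patient's remaining deviations still sum to zero.
- With one sample per patient, w_i1 = x_i1 − x_i1 = 0. A baseline-only comparison therefore has no data left.

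**Simulation.** Assumptions: 25 v 25 patients, 5 times, 600 features, within-patient correlation 0.5, 40 features kept per component, 200 runs. One component was used for the case/control and time labels, two for group-by-time. There were 20 features of each type: a 1 SD group shift at all times, a 1 SD group shift at times 2 to 4 only, and a 1 SD time effect only. Percentage selected:

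| Method and class label | Constant group shift | Group-by-time shift | Time only | Null |
|---|---|---|---|---|
| Multilevel, case/control | 0 | 0 | 0 | 0 |
| Multilevel, group-by-time | 3.2 | 99.98 | 100 | 2.8 |
| Multilevel, time | 0.1 | 97 | 100 | 0.1 |
| Ordinary, case/control | 98 | 56 | 0.7 | 1.7 |
| Ordinary, group-by-time | 97 | 98.5 | 100 | 1.4 |

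**Effect of the intersection.** In a separate run with the same patient numbers, feature count and correlation, a t-test on patient means with Benjamini-Hochberg control found 88% of the constant-shift features. In this model patient means and within-patient deviations are independent, so the share passing both is about:
- multilevel, group-by-time label: 0.88 × 0.032 = 0.028, or 2.8%;
- multilevel, time label: 0.88 × 0.001 = 0.0009, or 0.1%;
- ordinary sPLS-DA by group: between 0.88 + 0.98 − 1 = 0.86 and 0.88, or 86% to 88%.

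**Baseline alone.** In a second simulation (2,000 features, 20 of them shifted by 1 SD at all times, top 100 kept), ordinary ranking on the baseline sample kept 91% of the shifted features. The multilevel ranking of all samples kept 5%, which is chance: 100/2,000.

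**The case against.** The strongest reply is that the list is open. It is introduced as a set of examples, under a label about change across time points, for which a within-patient method is well suited. The biomarker step that follows asks for both kinds of approach without saying which. An analyst could add a between-patient selector and still follow the plan. This stands as a reason to call the gap one of specification. It does not remove the gap, because no such selector is named anywhere and the class label is missing.

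Several stronger readings are tempting, and the documents do not support them:
- *A reader might infer that the method cannot see case/control differences at all.* It detects differences in change over time when the classes are coded group-by-time (99.98% in the simulation).
- *That every stable signal is lost.* The targeted case/control tests of Aim 1.1, the metabolome-wide association analysis of specific metabolites, and the fallback to raw p-values for pathway enrichment are not subject to this filter. They are partial routes: the first two start from chosen metabolites, and the third applies only when a comparison yields no FDR-significant metabolite.
- *That Aim 2.3 fails in the same way.* Aim 2.3 compares changes by randomised arm, which is an arm-by-time question, and randomisation gives no reason to expect a constant difference that predates the dose.
- *That the Potential Pitfalls paragraph makes this loss central.* Its remark that "it is possible that pre-surgical elevation of biomarkers predicts the development of stress-hyperglycemia" concerns the path-specific biomarkers of Aim 1.1, which never enter the untargeted filter.
- *That the mixed models and Tukey tests compare time points only.* This is inferred from a label; the plan specifies no contrasts.

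It is also fair to say that Aim 1.2 is exploratory and that the Innovation section plans to reproduce findings in independent cohorts.

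**Conclusion.** The point holds in limited form. If the named methods are the ones run, case/control differences that are constant over time reach the Aim 1.2 consensus signature only by chance, and a baseline-only comparison is impossible with the named multivariate method. The cancellation is algebra and needs no assumption about effect size. The selection rates do depend on the assumed 1 SD shifts, the correlation of 0.5, the feature count and the number kept. The loss applies to the constant part of a difference: one that grows or fades after surgery can still be picked up as group-by-time.

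Severity is moderate. Only the exploratory untargeted analysis is affected, with no effect on the trial's primary endpoint or on safety.

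**What to change.** For case v control in Aim 1.2:
- Use ordinary (non-multilevel) sPLS-DA with class = case/control at named time points, baseline and intraoperative first. It may also be run on change from baseline, but change scores remove constant differences too, so that version answers the group-by-time question and cannot replace the single-time analyses.
- In LIMMA and the mixed models, test group and group-by-time contrasts with patient as blocking or random effect.
- Apply the consensus rule within each contrast.
- Keep multilevel sPLS-DA for within-patient time or group-by-time contrasts, and state the class label.

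For Aim 2.3 it is enough to state that the class is arm-by-time, or to use ordinary sPLS-DA by arm on change from baseline.

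The cost is analysis-plan wording, slightly more analysis, and more contrasts under false discovery rate control. No new patients or samples are needed. The change should be made before the metabolomics data are analysed.

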Analysis: Student's t test and χ^2 tests will be used when appropriate. Mann-Whitney U or Kruskal-Wallis nonparametric tests will be used for non-normally distributed variables. Analysis will account for age-matching. The relationship between biomarkers and stress-hyperglycemia and surrogates of insulin sensitivity and beta cell function will be determined using the Cox proportional hazards regression in unadjusted models and in models adjusted by gender, and smoking status to evaluate the impact of each 1 U increase in a biomarker risk score based on previously defined cut points for CRP, FDP, HSP-70, and suPAR (3 mg/L, 1.0 $\mu\text{g}/\text{mL}$, 0.313 ng/ml, and 3.5 ng/ml, respectively) as previously described.^{65,66,68}

1.2 Untargeted Analysis: Utilizing untargeted LCMS-derived high-resolution metabolomics (HRM) analysis we aim to identify additional candidate metabolites and new metabolic pathways associated with incident stress hyperglycemia during cardiac surgery. **Methods:** HRM analysis is a major component of my career development plan. Data analysis will be conducted under the supervision of [name]. Data Interpretation will be conducted under the guidance of [name] (expert in metabolism). I will also have local support from [name] for interpretation of metabolomics results, as well as statistical support from [name]. [name] will provide guidance for hands-on use of metabolomics tools. Co-mentors and collaborators are experts in the data management requirements of the LCMS-derived high-resolution metabolomics (HRM) analysis proposed in this project. Serial samples will be collected: at baseline (up to seven days before surgery), at 15 minutes (after cardiac bypass has started for on pump surgeries) or 2hrs after sternum incision (for off pump surgeries), 24hrs, 72-96hrs and 30 days after surgery. Plasma samples will be stored at -80°C until analysis. The methods use UPLC with ultra-high resolution mass spectrometry with a dual chromatography, dual ionization approach with each sample being analyzed with three technical replicates.¹²²⁻¹²⁴

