
1.3 Integrative Analysis: A metabolome-wide association study (MWAS) of specific metabolites will be conducted (using MetabNet) to facilitate detection of their related metabolic pathways and network structures in association with stress-hyperglycemia. In addition, we will use xMWAS¹³³ for integrative network analysis to find multilevel associations between glucose levels, metabolites and biomarkers.

Expected outcomes of Aim 1: During our analysis of candidate metabolites and discovery phase in Aim 1 we expect to find an association between candidate metabolites (i.e. BCAA, ceramides, acylcarnitines) and pathways associated with stress-hyperglycemia. We also expect to find an association between pathway-

[figure not shown]

Figure 7. Workflow for high-resolution metabolomics. Samples are processed and analyzed in triplicate using liquid chromatography coupled to ultra-high resolution mass spectrometry. Data extraction and quality assessment is automated with stringent quality control requirements. Data are analyzed with well-established univariate and multivariate methods, with false discovery rate adjustment as appropriate. Selected features are tested for pathway enrichment, and suspect metabolites are confirmed by coelution and MS/MS with authentic standards. Reference standardization is used for quantification of metabolites of interest. ([name], [name] et al)

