- **Group Assignment / Case Definition:** Clinically stable adults scheduled to undergo coronary artery bypass graft surgery (CABG) will be studied. For logistic purposes recruitment will favor assignment to the clinical trial in the beginning of the award period (Aim 2, N=60). We expect a total of 30 subjects will be randomized to each group (dulaglutide or placebo). Thirty patients assigned to placebo in the clinical trial will contribute to the cohort of patients to be included in the nested case-control study. Cases and controls will be categorized prospectively on arrival to the surgical intensive care unit (SICU) (Cases are defined as BG >140mg/dL on ICU arrival). To further avoid selection bias, 25 age-matched controls will be selected for comparison. Once the number of cases is completed, additional potential controls will be selected (+/- 3 years) based on the characteristics of the population of cases. If additional patients develop stress hyperglycemia no further samples will be collected. This design will allow for efficient recruitment from our cohort of CABG patients to allow substantial savings in cost and time.
- **Research Sites:** All human subjects' research will be performed on the campus of Emory University, Atlanta, GA, and at Emory Affiliated Hospitals. Sites include Clinical Research Units (CTSA) where samples will be stored. Data collected are kept confidential and protected as per HIPAA regulations. Data collected at each facility will be shared only with the study team.

E.1.2. Study Endpoints and Sources of Materials:

- In the case control study (Aim 1) we will compare metabolic and hormonal profiles between subjects that develop stress hyperglycemia compared to controls. In an open-label format (Aim 2) we will assess whether exposure to dulaglutide is associated with a reduction in the frequency of stress hyperglycemia compared to placebo (primary endpoint). Prospectively, we will assess the association of candidate metabolites and metabolic pathways with the onset of stress hyperglycemia. Potential mechanisms underlying these associations will be explored by examining whether the associations of exposure to dulaglutide and prevention/improvement of glycemic control can be explained by changes in metabolic pathways (and key metabolites within these pathways) measured in plasma that occur between 3 days prior to surgery (baseline) and during the perioperative period. Addressing these research questions

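### Aim 1.2 does not say that biomarker selection is repeated inside the SVM cross-validation folds; if it is done once on all 50 patients using case/control status, the reported accuracy would be biased upward

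*Combined protocol and SAP*

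**What the plan says.** The workflow is in D1, Aim 1.2 (Untargeted Analysis) of the combined protocol and SAP, and most of it is printed a second time shortly before the expected outcomes of Aim 1. The order is as follows.

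- Screening uses mixed models, LIMMA and multilevel sparse PLS-DA. "Multiple hypotheses testing correction will be performed using the Benjamini-Hochberg method", with no false discovery rate level given.
- A consensus rule follows: "metabolic signatures identified by both univariate and multivariate approaches will be used for downstream analyses".
- Then comes validation: "K-fold and leave-one-out cross-validation using Support Vector Machine (SVM) will be performed to evaluate predictive accuracy of putative biomarkers". K, kernel and tuning are not given.
- Hierarchical clustering is then used, among other things, "to evaluate the ability of the discriminatory features to separate samples based on stress-hyperglycemia".

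No section says that selection is repeated within training folds, that a test set is kept aside, or that folds are formed by patient. The workflow is referred to Fig. 7. The image is not available, and its caption mentions "Data are analyzed with well-established univariate and multivariate methods, with false discovery rate adjustment as appropriate" but not cross-validation.

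The pitfalls paragraph for Aim 1 covers comparisons in which nothing passes the false discovery rate: "metabolites with raw $p < 0.05$ will be used for subsequent analyses, with statistical tests for pathway enrichment".

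Aim 1 has N=50, of whom "25 age-matched controls will be selected for comparison". There are five sampling times, "each sample being analyzed with three technical replicates".

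**The concern.** Cross-validation estimates accuracy in new patients only if the held-out patients played no part in building the classifier, and choosing the features is part of building it. When thousands of features are screened against the outcome in 50 patients, those that pass do so partly because of chance differences in these same patients. If a patient is removed only after the list is fixed, the list still carries that patient's contribution.

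The SVM accuracy is the only cross-validated measure of prediction in the plan; the clustering check reuses the same features and samples. Item 6 of the Innovation section and E.1.6 look ahead to work in independent cohorts. What is at stake is how strong the candidate metabolites appear when they are carried forward, not any trial endpoint.

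**Working it through.** **The nearest planned figure.** The plan states no accuracy, so there is none to reproduce. E.1.9 justifies N=50 by an effect size above 1 (Wilcoxon test, alpha 0.05, power 0.80). For one two-sided test, n per group = 2(1.960 + 0.842)²/1² = 15.7, so 16; the t-test needs 17 and the Wilcoxon test about 18. With 25 per group the power is Φ(√(25/2) − 1.960) = Φ(1.576) = 0.94. The sample size is adequate for a single test. It also makes 1 SD the lower edge of the planned effect range.

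**Why passing the screen matters.** Benjamini-Hochberg accepts the k smallest p-values if p₍ₖ₎ ≤ qk/m. Take q = 0.05 (assumed), m = 2,000 and 25 vs 25 (48 df). The smallest observed difference that passes is t × √(2/25) SD:

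| Features passing (k) | p threshold | t | Observed difference needed |
|---|---|---|---|
| 1 | 0.000025 | 4.67 | 1.32 SD |
| 10 | 0.00025 | 3.96 | 1.12 SD |
| 50 | 0.00125 | 3.43 | 0.97 SD |

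When few features pass, one with a true effect of 1 SD must look larger than it is in these 50 patients. One with a true effect of 1.5 SD usually need not. The bias should therefore shrink with larger effects and with more real features.

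**Simulation.**

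- From the documents: 25 vs 25 (N=50 and 25 controls); 2,000 features (Aim 1.2) or 4,144 (preliminary data, C.6); the Benjamini-Hochberg method.
- Assumed: selection contrasts cases with controls; q = 0.05; t-test screen intersected with the top 10 PLS-DA weights; linear SVM with C = 1; one sample per patient; equal effects; the number of real features.
- Each setting has 300 data sets, averaged over those with at least one passing feature. New-patient accuracy is measured in 2,000 further patients.
- Bias = un-nested 5-fold accuracy − new-patient accuracy.

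| Real features | 1 SD | 1.25 SD | 1.5 SD |
|---|---|---|---|
| 5 of 2,000 | 0.806 − 0.708 = 0.098 | 0.873 − 0.828 = 0.045 | 0.926 − 0.910 = 0.016 |
| 10 of 2,000 | 0.859 − 0.777 = 0.082 | 0.931 − 0.902 = 0.029 | 0.974 − 0.966 = 0.008 |
| 20 of 2,000 | 0.917 − 0.849 = 0.068 | 0.974 − 0.949 = 0.025 | 0.990 − 0.979 = 0.011 |
| 10 of 4,144 | 0.852 − 0.753 = 0.099 | 0.928 − 0.889 = 0.039 | 0.970 − 0.963 = 0.007 |
| 10 of 2,000, correlation 0.5 | 0.783 − 0.703 = 0.080 | 0.798 − 0.754 = 0.044 | 0.821 − 0.801 = 0.020 |

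The Monte Carlo standard error of these differences is 0.001-0.005. Un-nested leave-one-out was within 0.005 of un-nested 5-fold throughout.

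**Sensitivity to the assumptions.** With 50 real features at 1 SD (60 data sets), the bias was 0.066 with the top-10 cap and 0.022 with a top-100 cap. With the top-100 cap at 1.5 SD it was 0.000. At q = 0.20 with the top-100 cap and 1 SD it was 0.009.

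**Effect of nesting.** For 10 of 2,000 at 1 SD, nested 5-fold gave 0.662, nested 10-fold 0.724 and nested leave-one-out 0.767, against 0.777 in new patients. Over the five 1 SD settings, nested 5-fold was 0.07-0.13 too low and nested 10-fold 0.04-0.07 too low. Nested leave-one-out was within 0.014 in all 15 settings. Training folds with no passing feature were scored 0.5, which adds to the K-fold shortfall.

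**The case against.** **The plan is silent rather than committed to un-nested selection.** K-fold and leave-one-out cross-validation can both be run with selection inside the folds, and the Fig. 7 procedures may do so. This stands: the point is what would follow from the written order, not what will certainly be done.

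**Selection may not use case/control status.** The screening methods are introduced as finding differences across time points. If selection used only time contrasts, case/control labels would not leak: a check with no group signal gave 0.52 (standard error 0.013). This stands as a condition. A case/control contrast is still the more natural reading, because Aim 1.2 seeks metabolites associated with incident stress hyperglycemia and the clustering sentence calls the list discriminatory.

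**The size is not fixed by the documents.** The false discovery rate level, number of real features, selection cap, kernel and K are all absent. Conditioning on at least one passing feature also drops up to 37% of the 1 SD data sets. This stands too, so a range is given rather than one figure.

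A reader might infer two stronger things. The first is inflation close to 0.5 when there is no signal. That needs the raw p<0.05 list to feed the SVM, and the pitfalls paragraph names only pathway enrichment for it. Under Benjamini-Hochberg alone, no-signal data passed any feature in only 5.2% (2,000 features) or 5.5% (4,144) of 1,500 data sets. In those rare cases un-nested accuracy was 0.756 or 0.780 against 0.50. The second is leakage of one patient across folds through time points or replicates. Nothing says that these enter the SVM as separate rows, and the only stated use of replicates in Aim 1.2 is data quality. Neither is counted here.

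Finally, E.1.9 gives the Aim 1 objective as identifying metabolites and pathways, and no accuracy threshold triggers a decision. That limits the importance of the point but does not remove it.

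**Conclusion.** The point holds in conditional form. The plan places selection before the SVM cross-validation and states neither nesting nor patient-level folds. If selection uses case/control status and is done once on all 50 patients, the reported accuracy would be biased upward.

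Under the stated assumptions, the bias is about 0.02-0.10 at 1 SD, smaller with more real features, and about 0-0.02 at 1.5 SD. These are illustrations: other choices of q or selection cap move the figures, and at q = 0.20 with many real features the 1 SD value falls below 0.02. Since planning is for effects above 1 SD, the upper part of the range belongs to the least favorable edge. The output is exploratory, and no endpoint of the randomized comparison depends on it.

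**What to change.** Add to Aim 1.2:

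- Every step that uses the outcome labels (univariate screen, msPLSDA, consensus selection, SVM tuning) is repeated inside each training fold.
- If more than one sample or replicate per patient enters the SVM, all of that patient's rows are held out together.
- The nested accuracy is the reported estimate, with K stated and a note that nested K-fold can err low at this sample size.

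Selection on the full data may still be used for pathway enrichment. It would help to confirm that the raw p<0.05 list is for enrichment only. A label-permutation check is a useful option, because in the rare no-signal data sets with a passing feature nested leave-one-out still read 0.60-0.61 against 0.50.

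The cost is two or three sentences, more computing time and a lower reported accuracy; no new patients or assays are needed. If the Fig. 7 procedures already nest selection, one sentence saying so is enough.
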